The Co-PIs recently reported the first human work directly examining associations between EO function and opioid analgesic responses. Using controlled laboratory methods, associations were examined between spontaneous EO function (indexed by differences in acute pain responses between opioid blockade [naloxone] and placebo conditions) and analgesic responses to morphine, the prototypic mu opioid agonist¹⁸. In a sample of 45 chronic low back pain patients and 31 pain-free healthy controls (combined for analyses given no significant main or interaction effects of subject type), significant associations were observed between EO function and morphine analgesic responses on all 7 measures of pain responsiveness examined across two different evoked pain tasks (ischemic pain, thermal pain)¹⁸. We recently extended these findings to clinical chronic pain¹⁹. Individuals exhibiting less EO inhibition of their chronic back pain (less effect of opioid blockade on back pain intensity) experienced greater relief of their back pain with morphine administration relative to higher EO individuals¹⁹. To isolate the source of the effects noted in Bruehl et al.¹⁸ and provide a clear means of portraying them, median splits were conducted on EO function variables derived for each pain measure, with placebo condition and morphine condition responses for each measure then compared across the resulting groups. The pattern of results indicated an intriguing source of these observed associations. First, as expected, when EO systems were intact (placebo condition), individuals exhibiting relatively lower spontaneous EO activity were significantly more responsive to both evoked pain tasks on all measures. Second, individuals with lower EO function exhibited substantial morphine analgesic responses whereas those with higher EO function did not.

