Lab Visit 1 (≈Day 7): Participants will undergo a urine screening for opiate use (females will also be screened for pregnancy); complete psychometric instruments; training for heat pain stimulus (Visit 1 only); 5 minutes of seated rest; participants rate their current low back pain intensity; nurse inserts i.v. cannula; nurse obtains a 4ml blood sample via cannula to assess endocannabinoid levels (Visits 1 and 4 only); nurse administers randomized drug dose #1. Administration of randomized drug dose #1 (specific drug protocol is summarized below) will be followed by 10 minutes of seated rest to achieve peak drug levels; participant rating of chronic pain intensity; thermal pain task #1 (described in detail below); assess thermal pain intensity; assess drug side effects and psychoactive effects; nurse administers randomized drug dose #2. Administration of drug dose #2 will be followed by 10 minutes of seated rest to achieve peak drug levels; participant rating of chronic pain intensity; thermal pain task #2; assess thermal pain intensity; assess drug side effects and psychoactive effects; nurse administers randomized drug dose #3. Administration of drug dose #3 will be followed by 10 minutes of seated rest to achieve peak drug levels; participant rating of chronic pain intensity; thermal pain task #3; assess thermal pain intensity; assess drug side effects and psychoactive effects; nurse administers randomized drug dose #4. Administration of drug dose #4 will be followed by 10 minutes of seated rest to achieve peak drug levels; participant rating of chronic pain intensity; thermal pain task #4; assess thermal pain intensity; assess drug side effects and psychoactive effects; seated rest until side effects remit.

(each session ≈ 5 days apart)

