Lab Visit 3: Participants will undergo a urine screening for opiate use (females will also be screened for pregnancy); 5 minutes of seated rest; participants rate their current low back pain intensity; nurse inserts i.v. cannula; nurse administers randomized drug dose #1. Administration of randomized drug dose #1 will be followed by 10 minutes of seated rest to achieve peak drug levels; participant rating of chronic pain intensity; thermal pain task #1; assess thermal pain intensity; assess drug side effects and psychoactive effects; nurse administers randomized drug dose #2. Administration of drug dose #2 will be followed by 10 minutes of seated rest to achieve peak drug levels; participant rating of chronic pain intensity; thermal pain task #2; assess thermal pain intensity; assess drug side effects and psychoactive effects; nurse administers randomized drug dose #3 . Administration of drug dose #3 will be followed by 10 minutes of seated rest to achieve peak drug levels; participant rating of chronic pain intensity; thermal pain task #3; assess thermal pain intensity; assess drug side effects and psychoactive effects; nurse administers randomized drug dose #4. Administration of drug dose #4 will be followed by 10 minutes of seated rest to achieve peak drug levels; participant rating of chronic pain intensity; thermal pain task #4; assess thermal pain intensity; assess drug side effects and psychoactive effects; seated rest until side effects remit.

Exercise Manipulation (Weeks 4 – 10 of study participation): Following the third laboratory visit, participants will be randomly assigned to study condition, stratified by recruitment source (clinic vs. community). Participants randomly assigned to the exercise condition will then complete the 18 session aerobic exercise manipulation supervised by an ACSM-certified personal trainer at the Dayani Center (3 exercise sessions per week for 6 weeks). Participants assigned to the control condition will not undergo any manipulation during this 6 week period, and will be asked to continue their current activity levels and not engage in any additional exercise activity during the study period (confirmed via electronic diary). All subjects will complete brief pain and psychosocial questionnaires once weekly by phone.

Lab Visits 4 – 6 (\approx Weeks 11-12): Identical procedures to those described above for Lab Visits 1-3. Drug order is again randomized and counterbalanced.

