Post-Manipulation 5 day Electronic Diary Monitoring Period (\approx Week 11, between Lab Visits 4-5): Identical to pre-manipulation electronic diary procedures described above.

Description of Laboratory Visit Procedures:

All laboratory procedures will be conducted with participants seated upright in a comfortable chair. Each participant's series of three laboratory sessions (placebo, naloxone, morphine) carried out both pre- and post-manipulation will be scheduled within an ≈ 10 day period, at the same time of day to control for variance due to circadian rhythms.

Study Drug Protocol: Study drugs will be administered (in double-blind fashion) in randomized, counter-balanced order. The assigned study drug will be administered within a given session over 4 infusions (2 min each) according to the following protocol, depending on the assigned drug for that visit: 1) 4 doses of saline placebo (20ml each), 2) an 8mg dose of naloxone (in 20ml saline vehicle), followed by saline, 4mg naloxone, and saline, or 3) morphine sulfate (0.03 mg/kg in 20ml saline vehicle initially, followed by 3 incremental doses of 0.02mg/kg each). To avoid excessive morphine doses (and increased side effect risks) for individuals who are obese, a modified weight adjustment will be employed for individuals more than 30% over ideal body weight based on subjects' observed weight in clinic compared to appropriate ideal body weight for males (50kg+2.3kg for each inch over 5 feet) or females (45.5kg +2.3kg for each inch over 5 feet) [from <http://www.globalrph.com/>]. For individuals meeting this obesity criterion, morphine dosage will be based on Adjusted Body Weight rather than actual body weight, as calculated by: $\text{Ideal Body Weight} + 0.4 (\text{actual weight} - \text{Ideal Body Weight})$.

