Blockade effect variables reflecting EO function will be derived by subtracting evoked pain responses during placebo from comparable responses during opioid blockade (separately for pre-manipulation baseline [BL] and post-manipulation). Given no theoretical rationale for expecting dose response effects with repeated dosing for placebo or naloxone conditions, we will average over the 4 pain stimuli within each of these drug conditions (separately for pre- and post-manipulation sessions) as a means of reducing random measurement error in deriving blockade effects. Blockade effects will be derived such that larger positive values reflect greater EO analgesia. To reduce number of variables, a mean value of the standardized EO function variables (blockade effects) will be derived and will be used initially in analyses (as in Bruehl et al.¹⁸). Chronic pain intensity pre- and post-manipulation will be defined as mean chronic pain ratings during the respective electronic diary sampling periods. As manipulation checks, we will determine whether degree of spontaneous EO function pre-manipulation is correlated significantly with evoked pain sensitivity and chronic pain intensity at BL. Total number of exercise minutes recorded during the post-intervention diary monitoring period (obtained in both groups) will be explored as a potential covariate for use in primary group analyses.

Primary Analyses.

Aim 1: To determine whether an aerobic exercise manipulation increases EO activity in CLBP patients, and whether these EO changes mediate manipulation-induced reductions in evoked pain responsiveness and daily CP intensity. We will conduct Group (exercise, control) x Time (BL, post-manipulation) mixed design ANOVAs to determine whether evoked pain sensitivity and CP intensity decreased significantly in the aerobic exercise group only. We will also conduct Group (exercise, control) x Time (BL, post-manipulation) mixed design ANOVAs on EO function (blockade effect variables pre- and

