post-manipulation) to determine whether EO function increased in the aerobic exercise condition only. We will then test whether group differences in pre- to post-manipulation EO changes mediate group differences in pre- to post-manipulation reductions in evoked pain responsiveness and CP intensity using the bias-corrected bootstrap mediation testing approach of Preacher and Hayes¹⁰⁰. This approach is statistically powerful and not dependent on any assumptions about the sampling distribution of the variables, and was used successfully in our recently published work¹⁸. Per Preacher & Hayes¹⁰⁰, the only precondition for testing mediation will be presence of an effect to be mediated (i.e., the exercise condition is associated with significantly greater reductions in evoked pain responses and CP intensity than the control condition). For any outcomes for which this precondition is met, bootstrap tests of mediation will proceed using the Indirect procedure for SPSS^{100, 101} (<http://www.afhayes.com/spss-sas-and-mplus-macros-and-code.html#sobel>) as in our recent work¹⁸. If the 95% CI for the indirect effect in a given model does not include zero, this will indicate that the hypothesized indirect (mediated) effect is significant at $p < .05$. In this case, a significant indirect path will indicate that the link between aerobic exercise condition and reduced evoked pain responsiveness or CP intensity is significantly mediated by exercise-related EO enhancements. Significant direct and indirect paths jointly for the same outcome will indicate partial mediation. A significant direct path in the absence of a significant indirect path will be interpreted as indicating that the effects of the exercise manipulation on that outcome are mediated via non-opioid mechanisms.

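### Aim 1 attributes the fall in diary back pain to endogenous opioids through a heat-pain mediator alone, and leaves unused the blinded naloxone-placebo contrast on back pain that every participant already provides

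*Combined protocol and SAP*

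**What the plan says.** **Mediator and outcome.** Under Data Reduction and Analyses, Section 10.0 builds the EO variable from heat pain: "Blockade effect variables reflecting EO function will be derived by subtracting evoked pain responses during placebo from comparable responses during opioid blockade". Responses are averaged over the four heat tasks in each session. Chronic pain (CP) intensity is the mean of the diary ratings, pre and post.

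**Inference.** Aim 1 under Primary Analyses first requires a significantly greater fall in CP intensity with exercise than with control. A bias-corrected bootstrap of the indirect effect follows. The plan states that "a significant indirect path will indicate that the link between aerobic exercise condition and reduced evoked pain responsiveness or CP intensity" is mediated by exercise-related EO enhancement if that path is significant. A significant direct path without a significant indirect path is to be read as a non-opioid mechanism.

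**Ratings collected.** In Section 6.0, every laboratory visit has a back pain rating before drug ("participants rate their current low back pain intensity; nurse inserts i.v. cannula") and one after each of the four infusions (from "participant rating of chronic pain intensity; thermal pain task #1" to "participant rating of chronic pain intensity; thermal pain task #4"). Visits 4 to 6 repeat this: "Identical procedures to those described above for Lab Visits 1-3". On allocation: "Study drugs will be administered (in double-blind fashion) in randomized, counter-balanced order".

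**Use of those ratings.** No primary or secondary analysis in Section 10.0 uses them, and no reason is given. Section 3.0 shows that the team has worked with a blockade effect on back pain before: "Individuals exhibiting less EO inhibition of their chronic back pain (less effect of opioid blockade on back pain intensity") had greater back pain relief from morphine.

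**The concern.** For heat pain, the plan makes the direct test: does the naloxone-placebo difference grow more with exercise than with control? Exercise is randomised between people and drug order within them. For back pain there is no such test. The EO explanation of the CP result depends on the path from heat-pain EO change to diary change (the b path). Randomising exercise does not protect that path, and it crosses two kinds of pain.

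Both of the plan's readings are therefore insecure. A significant indirect path can arise from any common cause of the two changes. A direct path alone can arise because heat-pain EO is a poor marker of opioid control of back pain, or because a real indirect effect was missed.

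At stake is one of the trial's main mechanistic conclusions: whether exercise relieves chronic back pain through endogenous opioids. If it does, naloxone should raise back pain relative to placebo by more after training than before, and more in exercisers than in controls. The data to examine this will already exist.

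**Working it through.** **1. The plan's own figures (Section 10.0).**
- d to r: 0.93/√(0.93² + 4) = 0.93/2.206 = 0.42, as stated.
- Exercise effect on EO, 58 per arm, d=0.93, two-sided 0.05: power 0.999, consistent with the stated value above 0.90.
- Mediation, N=116, a=0.42, b=0.26, simulated bias-corrected bootstrap: power 0.82 with unit-residual coefficients, and 0.77 to 0.83 across codings, against the stated 0.80.

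These figures stand, but they concern the heat-based mediator only. The b-path value of 0.26 corresponds to 0.26² = 0.068, about 7% shared variance.

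**2. Ratings available (Section 6.0).** Each session has 1 + 4 = 5 back pain ratings, so six sessions give 30. The two morphine sessions (10 ratings) play no part in a blockade contrast. The four placebo and naloxone sessions give 4 × 5 = 20: 16 post-dose and 4 pre-drug.

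**3. How often the planned rule would declare mediation when there is none.** Simulated trials had 58 per arm. With X the exercise indicator and U a shared cause:
- heat-pain EO change: M = 0.93X + √c·U + √(1−c)·e₁
- diary pain change: Y = −0.6X − √c·U + √(1−c)·e₂

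There is no path from M to Y, so the effect on back pain is wholly non-opioid. The values d=0.6 and c (the size of the residual correlation) are assumptions. The documents give neither. The test is the plan's: a significant group effect on Y, then the bias-corrected bootstrap.

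| Residual correlation c (assumed) | Mediation declared |
|---|---|
| 0 | about 5-8% |
| 0.1 | about 22% |
| 0.2 | about 58% |
| 0.3 | about 82% |

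At c=0.26, the size of the plan's own b path, the rate is about 75%. If exercise has no effect on heat-pain EO (a=0, c=0.3), claims in the hypothesised direction stay near 3-4%. Counting either sign, a check run of 1,500 trials gave about 7%.

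**4. The opposite reading.** At the stated power, a true indirect effect of the planned size is missed in 1 − 0.80 = 0.20 of trials. If the direct path is significant in such a trial, the plan would label the effect non-opioid.

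**5. Precision of the unused contrast.** Test Group x Time on the back-pain blockade effect, with d in SDs of its pre-to-post change. The documents give no effect size or SD for this, so d is a range.
- Detectable d = (z₀.₉₇₅ + z_power) × √(2/58). At 80% power: (1.960 + 0.842) × 0.1857 = 0.52. At 90%: (1.960 + 1.282) × 0.1857 = 0.60.
- Power at d = 0.2, 0.3, 0.4, 0.5 and 0.6: 0.19, 0.36, 0.58, 0.77 and 0.90.
- With 46 per arm (an assumed 20% loss), the detectable d is 0.58 at 80% power and 0.68 at 90%.

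**The case against.** **The plan's rule is stricter than it may look.** A reader might infer that a correlation between heat-pain EO change and diary change is enough to declare mediation. The documents do not support that. Section 10.0 requires a group effect on CP intensity first, and the indirect effect also needs an exercise effect on EO, which is a randomised comparison. Without that effect, false claims stay near the nominal rate. The weakness is confined to the b path and matters only if exercise does raise heat-pain EO. This stands.

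**The rates depend on assumed confounding.** Correlations of 0.2 to 0.3 bracket the whole planned b path, and any mediation analysis is open to a confounder that large. Nothing in the documents shows confounding of that size. This also stands: the table shows sensitivity and does not forecast an error rate.

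**The contrast cannot serve as an arbiter.** One might want to allow the EO claim only if the back-pain contrast agrees. With no opioid effect on back pain, the sign agrees by chance half the time, so a sign rule only cuts false claims from 58% to 29% and from 82% to 39%. A significance rule would block true claims, with power of 0.36 at d=0.3. Section 7.0 itself expects naloxone to have little or no effect on clinical pain. This stands and limits the remedy to a reported estimate.

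**It is a different quantity.** Aim 1 concerns daily pain, whereas these ratings are momentary and taken in a laboratory chair. The contrast complements the diary analysis and cannot replace it.

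None of this explains leaving the ratings unanalysed. The expectation in Section 7.0 is not offered as a reason, and it sits uneasily with the team's prior study result described in Section 3.0. If naloxone barely moves back pain after training, readers of an EO-mediation claim should be told.

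**Conclusion.** The point holds as an omission in the analysis plan. The power figures are not in error, and the randomised comparisons of exercise with control are unaffected, so a reader should not infer that Aim 1 is invalid. What is insecure is the step from a heat-based indirect path to a statement about how back pain fell, and equally the step from a missing indirect path to a non-opioid mechanism.

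The size depends on unmeasured confounding: from about 5-8% false mediation claims with none to about 82% at a residual correlation of 0.3. This is conditional on a real exercise effect on heat-pain EO (d=0.93) and a wholly non-opioid effect on back pain (d=0.6). The contrast that bears directly on the question is already in the design and goes unanalysed, although it may be imprecise.

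**What to change.** 1. Add a supporting Aim 1 analysis to Section 10.0. Define a back-pain blockade effect as mean post-dose back pain under naloxone minus placebo, at baseline and post-manipulation, with the pre-drug ratings as covariates. Test Group x Time, and report the estimate and 95% CI beside the heat-based mediation. Write out the model: on raw differences this equals Group x Time x Drug, but not automatically once each session is adjusted for its own pre-drug rating.
2. Set no gate on the sign or significance of this contrast.
3. Reword the Aim 1 conclusions. A significant heat-based indirect path is reported as consistent with EO mediation of CP intensity and read together with the back-pain contrast and its CI. A non-significant indirect path is not by itself taken as proof of a non-opioid mechanism.
4. State that the contrast concerns momentary laboratory back pain and complements the diary outcome.

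The cost is one model and some SAP wording, with no new visits or assessments. The drawback is a possibly wide CI, and a mechanistic claim that must be stated more cautiously.

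### In Aim 1 the EO mediator contains placebo-session evoked pain, so for that outcome the direct/indirect split can mislabel a fully opioid exercise effect

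*Combined protocol and SAP*

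**What the plan says.** Section 10.0, Data Reduction and Analyses, builds the mediator from two laboratory sessions. EO function is "derived by subtracting evoked pain responses during placebo from comparable responses during opioid blockade", separately before and after the manipulation. Within the placebo and naloxone sessions, "we will average over the 4 pain stimuli within each of these drug conditions". Across pain measures, "a mean value of the standardized EO function variables (blockade effects) will be derived" for initial use.

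Aim 1 first runs Group x Time ANOVAs to see whether "evoked pain sensitivity and CP intensity decreased significantly in the aerobic exercise group only", and the same ANOVA on the blockade effects. It then tests whether group differences in EO change "mediate group differences in pre- to post-manipulation reductions in evoked pain responsiveness and CP intensity", with a bias-corrected bootstrap. The gate is that "the only precondition for testing mediation will be presence of an effect to be mediated".

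Two reading rules follow. "Significant direct and indirect paths jointly for the same outcome will indicate partial mediation". A significant direct path without a significant indirect path is read as a non-opioid mechanism.

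The plan does not say which drug session supplies the Aim 1 evoked-pain outcome. Placebo is the natural reading: it is the only session with opioid systems intact and no drug given, and Aim 2 sets its 25% target against pre-exercise placebo responses.

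**The concern.** If the outcome is placebo-session pain, it sits inside its own mediator with the sign reversed. Someone whose placebo-session pain happens to fall by chance is automatically credited with a rise in EO function. That produces a b path from shared measurement, whether or not people with larger EO gains obtain more relief. Averaging four stimuli shrinks the session error but leaves the shared term in place, and so does standardizing and pooling measures.

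What is at stake is the statement about mechanism. The plan attaches substantive conclusions (partly opioid, or non-opioid) to the pattern of direct and indirect paths. For evoked pain that pattern depends largely on the relative variances of two sessions. The same section's manipulation check, which correlates baseline EO function with baseline evoked pain, has the same built-in link.

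**Working it through.** **Notation.** P and N are the pre-to-post changes in placebo-session and naloxone-session evoked pain, scored so that higher means more pain. The mediator is M = N - P. Let k = SD(N)/SD(P) and rho = corr(P, N), both within arm.

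**Inputs from the documents.** n = 116; a path d = 0.93 (r = 0.42); b paths r = 0.27 (morphine response) and r = 0.26 (diary pain); two-sided 0.05; power 0.80 (all Section 10.0). Half are assigned to exercise (Section 7.0), so 58 per arm. No b path is given for evoked pain. **Not given, so assumed:** k, rho, the between-person variance of EO change, and the correlations between pain measures.

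**1. The plan's own figure.** r = 0.93/sqrt(0.93² + 4) = 0.42. Simulating the bias-corrected bootstrap at n = 116 gives power 0.81 (b = 0.26) and 0.86 (b = 0.27), or 0.77 and 0.80 if these are read as zero-order correlations. The a-path power is 0.999. The stated 0.80 and the statement that a-path power exceeds 0.90 both reproduce.

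**2. The b path when the outcome is P.** Within arm,

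b = [cov(P,N) - var(P)] / [var(N) + var(P) - 2cov(P,N)] = -(1 - rho·k)/(1 + k² - 2·rho·k).

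With k = 1 this is -(1 - rho)/(2(1 - rho)) = -0.50 for every rho.

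**3. A fully opioid effect.** Exercise lowers P by delta and leaves N unchanged. Then a = delta, the total effect is -delta, and the indirect effect is b·delta. The estimated share mediated is therefore -b, where the truth is 100%.

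- k = 1: 50%.
- rho = 0.5, k = 0.8: 0.6/0.84 = 71%.
- rho = 0.5, k = 1.25: 0.375/1.3125 = 29%.
- rho = 0.8, k = 0.8: 0.36/0.36 = 100%. With k = 1.25: 0/0.5625 = 0%.
- True variation in EO change, with q = its variance divided by session-error variance: share = (q + 1)/(q + 2), so 67% at q = 1, 75% at q = 2 and 83% at q = 4.

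**4. How often the partial-mediation label appears** for that fully opioid effect, 58 per arm:

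- 0.8 SD effect, one measure, k = 1, rho 0.2 to 0.8: share about 50%; label in roughly 42-68% of trials.
- Same effect, rho = 0.5, k of 0.8 or 1.25, or q of 1 to 2: simulated share about 28-73% (formula 29-75%). Taken with the k = 1 cases, the label appears in roughly 18-78%.
- Three-measure standardized composite, k = 1: label in 27-63%. Another assumed set of cross-measure correlations gave 5-53%, with the non-opioid label in up to 27%.
- Full bootstrap with the plan's a path (d = 0.93), k = 1: label in 90%, 76% and 53% at rho 0.3, 0.5 and 0.7. At q = 1, rho = 0.5: share 66%, label in 40%.

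**5. If the outcome averages both sessions.** cov((P + N)/2, N - P) = (var N - var P)/2, which is 0 when k = 1. So b is about 0, and a fully opioid effect is labelled non-opioid in 42-66% of trials.

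**6. A wholly non-opioid effect.** P and N fall equally, so a is about 0. b is still -0.51, but the indirect path is significant in only 5.5% of trials.

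**7. The manipulation check.** With equal SDs and rho now the correlation between the two sessions' baseline levels, corr(P, N - P) = -sqrt((1 - rho)/2). That is -0.59, -0.50 and -0.39 at rho 0.3, 0.5 and 0.7, with no EO effect present.

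**The case against.** Several points on the other side stand.

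- **The test of opioid dependence is already planned.** With two levels per factor, Group x Time on naloxone-minus-placebo pain is the same contrast as Group x Time x Drug. What is missing is the reporting around it.
- **Half mediated is one assumed case.** It needs equal SDs and no true variation in EO change. Step 3 shows that other inputs can move the share to 100% or to 0%. The plan also schedules no estimate of the proportion mediated. It does schedule the labels, and those are what go wrong.
- **Overlap is not the only cause.** With an independent placebo session as outcome, the simulated share was lower still: 33% at q = 1 and 0% at q = 0. Error in the mediator understates mediation in its own right, so removing the overlap alone would not cure the split.
- **A naloxone-session outcome would not reproduce the problem.** A fully opioid effect leaves no group difference there, so the precondition would normally stop the mediation test.

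A reader might also infer that mediation would be found where none exists, because b is significant in 93-100% of simulated trials even when exercise acts wholly outside the opioid system. That does not follow: the indirect effect also needs the a path, and its false-positive rate stays near 5%.

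**Conclusion.** The concern holds for one outcome, Aim 1 evoked pain, on the reading that it comes from the placebo session. There the b path is partly built in, the indirect test adds little to the Group x Time test on EO function, and the partial-mediation rule can misdescribe a fully opioid effect. For one measure and a 0.8 SD effect, the share is about 50% in the equal-SD case and about 28-73% in the other cases at rho = 0.5, with the wrong label in roughly 18-78% of trials. These figures rest on assumed SDs and correlations and are not properties of the plan's data. Leaving the session unnamed makes matters worse, because an averaged outcome tends to give the opposite label.

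A reader might extend this to the whole mediation programme. The documents do not support that. Diary pain shares no session with the mediator. The power figure rests on the morphine and diary b paths and reproduces. Aim 2's target uses pre-exercise placebo pain, but no effect on Aims 2 or 3 has been shown. This should be fixed before analysis; it does not undermine the design.

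**What to change.** For evoked pain in Aim 1:

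- Name placebo-session pain as the outcome.
- Drop the a x b model and the partial-mediation and non-opioid labels.
- State that the planned Group x Time ANOVA on blockade effects is the test of opioid dependence, equivalent to Group x Time x Drug (placebo, naloxone).
- Report the Group x Time effect under placebo (total) beside that under naloxone (non-opioid part), with a bootstrap confidence interval for the share removed, 1 - (naloxone effect / placebo effect).

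Keep the mediation model for diary pain intensity, with a note that error in the mediator can understate mediation there too. State that the baseline correlation of EO function with evoked pain carries a built-in component and does not validate the measure.

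The cost is SAP wording and one added analysis of data already collected, with no new visits or participants. The downside is that evoked pain no longer has an a x b statistic.
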